### Searching for predictive biomarkers

Based on our and others studies, we have defined a pool of candidate prognostic biomarkers. We expect that some of these markers are also predictive. Thus, we would consider these markers as our top tier candidate predictive markers. First, we will follow the recommendation by Janes et al, and use the marker-by-treatment predictive curves using 1-year PFS (or 1-year OS) as the "response rates" to evaluate the interaction between the marker and the treatment. Only the markers with a qualitative interaction with the treatment will be further investigated, since they are the only markers that could guide the choice of treatments. We will dichotomize marker around the point where the two predictive curves cross. To test the interaction between the marker and treatment, we will fit the Cox proportional hazard model of the following form:  $\lambda(t) = \lambda_0(t) \times \exp\{\beta_1 Md + \beta_2 T + \beta_3 T * Md + \sum \beta_i \text{Covariates}\}$ , where Md denotes dichotomized marker value, T denotes treatment (HDI/HIP/LIP), the function  $\lambda(t)$  represents the event rate at time t, and  $\lambda_0(t)$  represents the corresponding baseline event rate. Likelihood ratio test will be used to test the null hypothesis of  $\beta_3=0$ . To adjust for the multiple testing, the Benjamini and Hochberg's (BH) method will be used to control the false-discovery rate (FDR) at 5%. We may also consider the risk score from the prognostic models developed above as a continuous marker and analyze them in the same way as described above. Markers (and risk scores) that show a significant qualitative interaction with the treatment effect will be further ordered by the estimated 1-year RFS (or OS) rate under the marker-policy. The top few (<5) predictive biomarkers may be validated in the

validation set. Given the lack of preliminary data on predictive biomarkers, if our search among the top tier markers failed, we will consider a genomic scan of gene expression to search for potential predictive biomarkers using the same strategy described above in the training dataset.

We will also consider building a multi-marker prediction model. Given the limited sample size, we will consider only the top 3-5 markers in the model. We will first fit a CoxPH model with main effects of the markers and the clinical factors:  $\lambda(t) = \lambda_0(t) \times \exp\{\sum \beta_i M + \sum \beta_i \text{Covariates}\}$ , and test the predictive value of the predicted risk score (the linear combination of this model) as described above.

The top few ( $\leq 5$ ) predictive markers (and/or panels) will be validated in the validation set. The same cutoff point will be used to dichotomize the marker value (or risk score value). CoxPH models with interaction term between the dichotomized marker and the treatment will be fitted. We will compare the direction and magnitude of the interaction term to that obtained in the training set. Likelihood ratio tests will be used to test the interaction of each marker and the treatment effects. A p-value of 0.01 (0.05/5) will be considered statistically significant.

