### XIX.9 Statistical Analysis Plan

- Statistical methods for the main analyses: For the single marker association with PFS and OS, Cox proportional hazards (CoxPH) regression will be used. Because some long-term cures have been observed in patients with stages IIB – III melanoma treated with HDI and ipilimumab, we will also perform exploratory analyses using a cure-rate model for RFS as a supplement to the CoxPH regression analyses proposed above. For multi-marker prognostic model, both the Lasso Cox proportional hazard regression and the Cox proportional hazard regression will be used. And the results will be compared.
- Transformations applied to variables: Distribution of data of different types will be checked and appropriate transformation will be used when necessary.
- Methods for marker cutpoint determination: For the predictive biomarker, we will follow the recommendation of Janes et al 2013 and use the marker-by-treatment predictiveness curves to guide the dichotomization of the marker (or risk score for multi-marker panel). Specifically, we will dichotomize the marker (or score) around the point where the two predictive curves cross.

- Variable selection procedures: We will use two strategies and compare our results: Cox proportional hazard regression with forward regression and Lasso Cox proportional hazard regression.
- List of standard clinical variables to be incorporated into models or other analyses: Clinical variables that we will consider to be included in the models are age, sex, Breslow thickness, recurrent disease at study entry, ulceration of the primary tumor, lymph-node status, number of positive lymph nodes, completion of lymph node dissection prior to treatment, microscopic extranodal extension, and mitotic rate in the primary tumor.
- Multiple-comparisons adjustment methods: To adjust for the multiple testing, the Benjamini and Hochberg's (BH) method will be used to control the false-discovery rate (FDR) at 5% for all candidate marker analyses. For the whole genome scan, we will use the procedure described in Storey 2002 to control the FDR at 5%.

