### Secondary Objectives

For the predictive biomarker analysis, again we will randomly split the samples into two groups of equal size, using one of them as the training set and the other one as the validation set. However, to avoid over fitting, the validation set will be held out till the last stage of the study, where it will be used to validate the few (<=5) final biomarkers (or panels).

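### The training-set screen for predictive markers filters, cuts and tests on the same patients, so its 5% FDR is not assured and true markers are lost

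*Combined protocol and SAP*

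**What the plan says.** Appendix XIX, section XIX.9, sets out the predictive-marker search under *Searching for predictive biomarkers*. The steps, in order, are:

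1. Draw marker-by-treatment curves of 1-year PFS or OS to assess the interaction.
2. Filter: "Only the markers with a qualitative interaction with the treatment will be further investigated".
3. Cut: "We will dichotomize marker around the point where the two predictive curves cross". The cut-point bullet in XIX.9 says the same: "we will dichotomize the marker (or score) around the point where the two predictive curves cross".
4. Fit a Cox model with treatment, dichotomized marker, their product and covariates. "Likelihood ratio test will be used to test the null hypothesis of" a zero interaction coefficient.
5. Adjust: the BH "method will be used to control the false-discovery rate (FDR) at 5" per cent.
6. Order the significant markers by estimated 1-year outcome under the marker policy and take the top few to validation.

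All of this happens in the training half: "the validation set will be held out till the last stage of the study". In validation the training cut-point is reused, at most five markers or panels are tested, and each is judged at 0.01. If the search among the first-tier candidates fails, a genome-wide expression scan follows with the same strategy.

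The search subsection does not say whether BH counts every candidate or only those that reach the Cox test. The multiple-comparisons bullet in XIX.9 applies BH to all candidate marker analyses, which could mean either.

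**The concern.** BH controls the FDR when null p-values are valid. Here they are not, for two reasons. A marker reaches the test only if its fitted curves cross, which is a condition on the estimated interaction, the quantity then being tested. The cut is also placed where that same estimate puts it. Neither step is corrected for.

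The plan recognises this problem elsewhere. Its primary-objective analysis keeps feature selection inside the cross-validation loop to prevent over-fitting, and it models markers without dichotomizing them. The predictive screen has neither safeguard.

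Three things are at stake: a shortlist described as having a 5% FDR when it may not, true markers discarded in training that validation cannot bring back, and a spurious first-tier hit that prevents the genomic-scan fallback from being triggered.

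**Working it through.** **Inputs from Appendix XIX.** Each half has 300 HDI and 250 ipilimumab patients before losses, with 80% specimen availability and 95% assay success: 550 × 0.80 × 0.95 = 418 (228 HDI + 190 ipilimumab). Treatment HR is 0.75, HDI hazard 0.917 per year, exponential RFS, accrual 40 months, minimum follow-up 12 months, and tests are two-sided.

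The 0.917 comes from a stated HDI median of 0.756 year. That median does not follow from the plan's own cure model: ln(0.71/0.21)/1.423 = 0.856 year, giving a hazard of 0.81. The stated 0.917 was kept to match the plan's power table, and the simulations were not rerun at 0.81.

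**Assumptions.** The documents give no candidate total. The lists in XIX.2 count to 11 cellular + 25 serum + 32 genes + 7 immunohistochemistry = 75; 30 and 60 were also tried. The number of truly predictive markers is unknown and was varied. Markers are standard normal. A crossing counts if at least 2%, 5%, 10% or 20% of patients lie on each side.

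**Reproducing the plan's figure.** For a 50% stratum and a ratio of HRs of 2.101, the plan states power 0.80. The formula is Power = Φ(√[N(ln Δ)² / Σ 1/(e·f)] − z₀.₉₉₅).
- Event probabilities under uniform accrual are 0.894, 0.853, 0.705 and 0.865.
- Σ 1/(e·f) = 4.10 + 4.29 + 6.25 + 5.09 = 19.73.
- N(ln Δ)² = 418 × 0.742² ≈ 230.3.
- √(230.3/19.73) = 3.416, and Φ(3.416 − 2.576) = 0.80.

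All 16 rows of the table reproduce within 0.01. They describe the validation test only; the plan gives no power or FDR calculation for the screen.

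**Why the filter selects on the tested quantity.** With a logistic model of the 1-year event, the curves cross at c = −b_T / b_TM. For a standard normal marker and a 10-90% window, retention needs |c| < 1.28, that is |b_TM| > |b_T|/1.28. When treatment has an overall effect, a null marker passes only if its chance interaction is large.

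**Simulated screen** (mostly 1,000-1,500 trials per scenario, N = 418). The retained marker is cut at c and tested by Cox likelihood ratio. The comparator is the Cox test of the continuous interaction on every candidate with BH.

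Training FDR, BH over retained markers only:

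| Setting | FDR |
|---|---|
| 75 candidates, none predictive, HR 0.75 | 15.2 / 17.4 / 19.7 / 16.2% for the 2/5/10/20% windows |
| Same, null markers correlated 0.3 | 13.7-17.6% |
| None predictive, HR 1.0 | 9.1-14.0% |
| 1 true of 75 | 11-15% |
| 2 true of 75 | 9-13% |
| 5 true of 75 | 8-10% (linear), 11-13% (step) |
| 10 true of 75 | 6-8% |
| 3 true of 30 | 5-8% |

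In the first setting a retained null marker has p < 0.05 in 8.8-11.2% of cases. A separate simulation with 60 candidates and the 10-90% window gives 18% with no true marker, 16.5% with one and 11% with five.

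BH over all 75 candidates, none predictive: 2.6-4.9% at HR 0.75 and 5.0-6.5% at HR 1.0. With 60 candidates and 1-5 true markers it is 4-7%. Comparator with 75 candidates: 5.6% with none true and 5.4% with five.

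Power per true marker. The main linear effect is set so that a median split has a ratio of 2.1: ln 2.101 = 0.742, the two half-means of a standard normal differ by 1.596, and 0.742/1.596 = 0.465 log-HR per SD.

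| Effect | Screen, BH over retained | Screen, BH over all | Continuous, all candidates |
|---|---|---|---|
| Linear, 0.465 per SD | 0.48-0.55 | 0.32-0.35 | 0.77 |
| Linear, 0.3 per SD | 0.14-0.19 | 0.06-0.07 | 0.27 |
| Step at the median | 0.15-0.20 | not tabulated | 0.24 |

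**Validation step.** Five independent tests at 0.01 give 1 − 0.99⁵ = 0.049.

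**The case against.** The strongest reply is that the screen is only a filter. The plan labels predictive modelling a secondary objective with limited preliminary data. At most five markers go forward to untouched patients with a frozen cut, each judged at 0.01, for a family-wise error of about 4.9%. That stands: validated claims are protected.

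A reader might infer that the plan's FDR simply is 16-19%. The documents do not support a fixed figure. It requires BH over survivors only, which the search subsection does not state and the multiple-comparisons bullet may contradict. It also requires few or no predictive markers, whereas the plan expects some, and an overall treatment effect.

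A reader might also infer that false markers fill the validation slots. In 300-run simulations with 60 candidates, more than five markers passed in at most 1.0% of runs, and false selections averaged 0.25-0.36 per run. The 0.01 threshold does not change with the number validated. The slot argument fails.

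Finally, the power comparison favours a linear effect, while the plan's own power model has two strata. For a step at the median the continuous test gains little (0.24 against 0.15-0.20), and a median split reaches 0.47. With the linear effect the screen with BH over retained markers slightly beats a median split (0.48-0.55 against 0.45). The loss is therefore relative to the continuous test and depends on the shape of the effect.

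**Conclusion.** The concern holds in limited form. As written, the screen does not assure a 5% FDR in the training half, and each reading of the BH denominator has a cost. Counting only retained markers, which is the natural reading because discarded markers get no Cox p-value, inflates the FDR. Counting all candidates roughly holds it but loses more true markers. Under both readings, power was below that of the continuous test in the linear-effect comparisons.

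The sizes rest on 30-75 assumed candidates, normal markers, logistic-linear curves and an assumed crossing window, none of which the plan specifies, and on HR 0.75 except where stated. The direction is secure; no single percentage should be attributed to the plan. The harm is a mislabelled shortlist, true markers lost before validation and a fallback scan that may not be triggered. It does not extend to the validated claims or to the trial's RFS and OS comparisons.

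**What to change.** Amend *Searching for predictive biomarkers* and the matching cut-point and multiple-comparisons bullets in XIX.9:

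- For every candidate, fit the Cox treatment-by-marker interaction with the marker continuous, transformed as XIX.9 already allows.
- Apply BH at 5%, and state that the denominator is all candidates tested.
- Only for markers that pass, use the curves to check for a crossing and to choose the cut-point, which goes unchanged into validation.

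Apply the same order to the genomic-scan fallback, which inherits this strategy. If a threshold effect is thought likely, a cut fixed before the outcome data are examined could be added as a declared sensitivity analysis.

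The cost is about one paragraph of Appendix XIX. No new samples, assays or follow-up are needed, and the requirement for a qualitative interaction, the crossing cut-point and the validation step all remain.

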**Primary Comparison**

The primary objective of the study is to build a prognostic model using the candidate biomarkers for each study arm. The secondary objectives are (a) to test for the therapeutic predictive power of prognostic panels discovered; (b) to search for

therapeutic predictive markers to guide the therapeutic choice of either ipilimumab or HDI; (c) to test for association of pre-specified genetic variants and the occurrence of colitis.

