### Power Calculation for Predictive Modeling

The goal here is to determine whether there is a significant difference between the clinical benefits of patients in different marker strata. That is, we are testing the interaction of the dichotomized marker value (we discuss how to dichotomize the marker value in details in our analysis plan in the following section) and the treatment group. We calculate our power based on the method by Peterson and George.

We denote the hazard function for each patient subgroup as the following:

	Marker stratum 1	Marker stratum 2
HDI	$\lambda_{11} = \lambda(t)$	$\lambda_{12} = \lambda(t)\lambda_{\text{Marker}}(t)$
Ipilimumab	$\lambda_{21} = \lambda(t)\lambda_{\text{Ipi}}(t)$	$\lambda_{22} = \lambda_{\text{Ipi}}(t)\lambda_{\text{Marker}}(t)\lambda_{\text{Interaction}}(t)$

where

$\lambda(t)$  is the baseline hazard

$\lambda_{\text{Ipi}}(t)$  is the hazard for the Ipilimumab group

$\lambda_{\text{Marker}}(t)$  is the hazard for marker stratum2 and

$\lambda_{\text{Interaction}}(t)$  is the hazard for the treatment by marker stratum interaction.

Denote  $N$  the sample size,  $f_{ij}$ , the number of subjects in treatment group  $i$  and marker stratum  $j$ , and  $e_{ij}$ , the event probability in treatment group  $i$  and marker stratum  $j$ . Define that  $\Delta = \frac{\Delta_1}{\Delta_2} = \frac{\lambda_{11} / \lambda_{21}}{\lambda_{12} / \lambda_{22}}$ , then the power to test the null hypothesis of  $\Delta = 1$

can be calculated using the following formula:

$$\text{Power} = \Phi^{-1} \left( \sqrt{N(\log \Delta)^2 / \sum \frac{1}{e_{ij} f_{ij}}} - Z_{1-\alpha/2} \right)$$

- $\alpha = 0.01$  : we do not intend to validate more than 5 predictive markers (and/or panels) in the validation set, thus, our type I error is set at  $0.05/5=0.01$ . All tests will be two-sided.

- For the purpose of power calculation, we assume the RFS time follows an exponential distribution.
- N: 250 on the ipilimumab arm + 300 on the HDI arm. We expect that we will be able to obtain samples from approximately 80% of the subjects. We expect that the assay success rate is at least 95%. Thus N is estimated to be 418.

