The following table listed the power for different marker stratum 1 frequencies ( $g_1$ ), and different effect sizes. We only considered marker with qualitative interaction with the treatment, assuming that patients in marker stratum 1 benefit from the ipilimumab and those in marker will benefit from HDI. Thus, we consider the situations where  $\lambda_{11} > \lambda_{21}$  and  $\lambda_{12} < \lambda_{22}$  only. We set  $\lambda_{11}$  and  $\lambda_{21}$  within the range of 0.7-1.2. The SWOG webtool (<http://stattools.crab.org>) was used for the power calculation. Here we assume the accrual time is 40 months (Accrual=40/12=3.3), minimum follow up is 12 months (Follow=12/12=1), Cell Freq Treat1/Strat1=  $f_{11}$ , Cell Freq Treat1/Strat2=  $f_{12}$ , Cell Freq Treat2/Strat1=  $f_{21}$ , Cell Freq Treat2/Strat2=  $f_{22}$ , Hazard Rate Treat1/Strat1= $\lambda_{11}$ , Hazard Rate Treat1/Strat2= $\lambda_{12}$ , Haz Ratio T1/T2 STrat1= $\Delta_1$ , and Haz Ratio T1/T2 Strat2= $\Delta_2$ .

Table 1 Power calculation for test of interaction ( $\alpha = 0.01$ , two-sided)

Marker stratum I Freq. (g i )	$f_{10}$	$f_{12}$	$f_{13}$	$f_{17}$	$\lambda_{11}$	$\lambda_{12}$	$\lambda_{13}$	$\lambda_{17}$	$\Delta_1$	$\Delta_2$	$\Delta$	Power
0.5	0.273	0.273	0.227	0.227	1.1	0.734	0.6	0.776	1.833	0.946	1.938	0.69
					1	0.834	0.5	0.876	2	0.952	2.101	0.8
					1.15	0.684	0.6	0.776	1.917	0.881	2.174	0.84
					1.05	0.784	0.5	0.876	2.1	0.895	2.346	0.91
					1.15	0.684	0.55	0.826	2.091	0.828	2.525	0.95
0.6	0.327	0.218	0.273	0.182	1.2	0.634	0.5	0.876	2.4	0.724	3.316	1
					1.05	0.718	0.6	0.82	1.75	0.875	2	0.72
					1	0.793	0.55	0.895	1.818	0.885	2.053	0.76
					0.95	0.868	0.5	0.97	1.9	0.894	2.124	0.8
					1	0.793	0.5	0.97	2	0.817	2.448	0.93
0.7	0.382	0.164	0.318	0.136	1.1	0.643	0.5	0.97	2.2	0.662	3.321	1
					1	0.723	0.6	0.893	1.667	0.81	2.058	0.69
					1.2	0.257	0.8	0.427	1.5	0.602	2.494	0.79
					1	0.723	0.55	1.01	1.818	0.716	2.539	0.92
					1.15	0.373	0.7	0.66	1.643	0.566	2.904	0.95
					1.05	0.607	0.5	1.127	2.1	0.538	3.9	1

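### Held-out validation of predictive markers tests for any treatment interaction, which does not by itself support a claim that a marker guides patients to HDI rather than ipilimumab

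*Combined protocol and SAP*

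**What the plan says.** The aim is set in Appendix XIX.8, Primary Comparison: one secondary objective is to look for "therapeutic predictive markers to guide the therapeutic choice of either ipilimumab or HDI". Appendix XIX.9, Searching for predictive biomarkers, restricts attention to markers with a qualitative interaction, "since they are the only markers that could guide the choice of treatments". The next step takes up this group: "Markers (and risk scores) that show a significant qualitative interaction with the treatment effect will be further ordered". The power section describes its alternatives in the same way: "We only considered marker with qualitative interaction with the treatment". Stratum 1 is assumed to do better on ipilimumab and stratum 2 on HDI.

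In training, crossing of the marker-by-treatment curves is used to screen markers and set the cutpoint. The interaction coefficient (beta3) is then tested by likelihood ratio with false-discovery control, and survivors are ranked.

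In the held-out half, five or fewer locked markers go forward. The analysis there is: "Likelihood ratio tests will be used to test the interaction of each marker and the treatment effects". The threshold is "A p-value of 0.01 (0.05/5) will be considered statistically significant", and for sidedness, "All tests will be two-sided". The one other check is "We will compare the direction and magnitude of the interaction term to that obtained in the training set".

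The two power sections (XIX.8, Power for Predictive Modeling, and XIX.9, Power Calculation for Predictive Modeling) give the goal more weakly, as detecting a difference in clinical benefit between marker strata.

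**The concern.** The null of the likelihood ratio test is that the ipilimumab-versus-HDI hazard ratio is equal in the two strata. That null is also false when ipilimumab is better in one stratum and equal, or somewhat better, in the other. Such a marker has no group that gains from HDI, yet it can pass validation.

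Comparing the direction and size of the interaction term with training does not help, because that term is a ratio of hazard ratios and says nothing about whether either one exceeds 1. The crossing is judged only in the training half, where the marker and its cutpoint are also chosen. The feature the plan says is needed for treatment choice is therefore neither tested nor explicitly reported on held-out data.

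At stake is a marker reported as directing some patients to HDI when no subgroup does better on it, and an optimistic view of how readily a true reversal could be shown.

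**Working it through.** **Inputs (Appendix XIX.9, Power Calculation for Predictive Modeling).** Validation N = 550 × 0.80 × 0.95 = 418; allocation 300/550 HDI and 250/550 ipilimumab; accrual A = 3.3 years; minimum follow-up F = 1 year; exponential times; HDI hazard 0.917; overall HR 0.75; stratum 1 share g from 0.5 to 0.7; two-sided alpha 0.01.

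**Formulas.** Event probability e(λ) = 1 − [exp(−λF) − exp(−λ(F+A))]/(λA). Events per cell = N × f × e. SE of log Δ = √(sum of 1/events over the four cells). Power = Φ(|log Δ|/SE − 2.576).

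**Reproducing Table 1.** Second row: g = 0.5, hazards 1, 0.834, 0.5, 0.876.
- Events are 101.8, 97.2, 66.8 and 82.1, so SE = 0.217.
- log 2.101 = 0.742; 0.742/0.217 − 2.576 ≈ 0.84; Φ = 0.80, as printed.
- All 16 rows reproduce to within 0.01.

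**No HDI-favouring stratum.** Same inputs, with HDI hazard 0.917 in both strata and overall HR held near 0.75. For the first line below, events are 99.7, 99.7, 64.0 and 83.1; SE = 0.218; log 2 = 0.693; Φ(3.17 − 2.576) = 0.725.

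| Split | Ipilimumab/HDI HR, strata 1 and 2 | Interaction test passes at 0.01 | Gail-Simon at 0.01 |
|---|---|---|---|
| 50/50 | 0.50, 1.00 | 0.725 | 0.010 |
| 50/50 | 0.55, 0.95 | 0.476 | 0.004 |
| 60/40 | 0.62, 0.95 | 0.265 | 0.004 |
| 70/30 | 0.66, 0.95 | 0.156 | 0.004 |
| 50/50 | 0.65, 0.85 | 0.091 | below 0.001 |

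For two strata, Gail-Simon at 0.01 requires stratum z-values of opposite sign, both beyond 2.326.

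**Checks on the first four lines.**
- Simulated Cox likelihood ratio tests gave 0.733, 0.475, 0.265 and 0.164.
- Under the protocol's cure model (cured fraction 0.29, uncured median 0.487 years) the simulated rates were 0.560, 0.335, 0.213 and 0.095.
- If the marker is also prognostic and stratum 2 has HR exactly 1, the range over the scenarios run was 0.07 to 0.72.
- With no interaction, simulation gave 0.013, so the test holds its level for its own null.
- The hazard 0.917 rests on a printed HDI median of 0.756 years. The stated cure model gives log(0.71/0.21)/1.423 = 0.856 years, hence hazard 0.810. With stratum 2 at HR 1 this moves the rates only from 0.725, 0.453, 0.251 to 0.701, 0.434, 0.239 (g = 0.5, 0.6, 0.7).

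**Adding the training half** (assumed equal in size and independent).
- Requiring only that the estimated effects cross gives joint rates of 0.36, 0.17, 0.10 and 0.06 for the first four lines.
- Adding a training interaction p below 0.01 gives 33%, 14%, 6% and 2%; below 0.001, it gives 25%, 8%, 2% and 0.7%.
- The actual false-discovery threshold depends on the data. Ranking and the cutpoint search are not modelled, and the cutpoint search could raise the rate.

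**Power to show a reversal at Table 1's effect sizes.** Second row: stratum 2 has log(0.834/0.876) = −0.049, SE = √(1/97.2 + 1/82.1) = 0.150, expected z = −0.33; stratum 1 has expected z = 4.40. Gail-Simon power is Φ(4.40 − 2.326) × Φ(0.33 − 2.326) ≈ 0.98 × 0.023 = 0.02, against the printed 0.80. Over the 16 rows the range is 0.02 to 0.80, with 10 rows below 0.15.

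**The case against.** The test matches the aim written beside it. Both power sections speak of a difference in benefit between strata, and the validation text never says that p < 0.01 proves a reversal. This stands. A reader might infer that the likelihood ratio test is invalid or breaches its 1% level; the documents do not support that, because the plan never assigns that level to the null of no HDI-favouring stratum.

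A reader might also infer that Table 1 is mislabelled. Its title already calls it a test of interaction. What is missing is a statement that these powers do not extend to showing the reversal assumed in every row.

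A marker without reversal can still be useful: section 11.1 gives the purpose of sampling as directing treatment to likely beneficiaries and sparing others toxicity and cost. That is fair, but Searching for predictive biomarkers takes the narrower view that only qualitative interactions count for treatment choice.

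The high rates hold near the boundary, for markers that have already passed training. With the second hazard ratio at 0.85 and a 50/50 split, crossing plus validation gives about 1%. This stands too, and rules out a claim that every marker lacking an HDI-favouring stratum is validated far above 1%.

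A compulsory Gail-Simon gate is debatable given its power here. Finally, this is a secondary objective, and no primary trial analysis depends on it.

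**Conclusion.** The concern holds in limited form. Held-out validation supports the statement that the treatment effect differs by marker; it does not support the statement that a marker selects patients for HDI, because no stated held-out step examines a reversal. Near the boundary (one stratum at HR 0.95 to 1.00, none favouring HDI), a marker that reaches validation passes about 15% to 72% of the time in the four cases with equal HDI hazards across strata, and about 10% to 56% under the cure model. The rate is about 9% or less when ipilimumab is clearly better in both strata. No single joint error rate can be given, because the training screen, false-discovery control and ranking reduce it by an amount that rests on assumptions. These figures assume N = 418, the plan's allocation and follow-up, and overall HR near 0.75.

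**What to change.** In Searching for predictive biomarkers, for each locked marker, report the validation-set ipilimumab-versus-HDI hazard ratio with confidence interval in each stratum at the locked cutoff. With HDI and one stratum as reference, these come from beta2 and beta2 + beta3 of the Cox model already planned. Describe a significant likelihood ratio test as evidence that the treatment effect differs by marker. Call a marker treatment-guiding towards HDI only if the held-out stratum results support a reversal; a Gail-Simon test is one optional way to show this.

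In both power sections, state that the Table 1 powers are for any interaction, and that power to show a reversal at the same effect sizes is about 0.02 to 0.80 (Gail-Simon, 0.01).

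The cost is a few sentences and two estimates per marker, with no new data. The downside is that fewer markers will qualify as treatment-guiding, and the stated power for that claim becomes less favourable.
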